The BELLINI study (Study M14-031), a global, Phase 3, multicenter, randomized, double-blind study of bortezomib and dexamethasone in combination with either venetoclax or placebo in subjects with R/R MM who are sensitive or naïve to proteasome inhibitors, was unblinded as per protocol for the final analysis of the primary efficacy endpoint. As of the data cutoff date of 26 November 2018, 194 subjects were randomized to the venetoclax arm and 97 subjects to the placebo arm (2:1 randomization). The BELLINI study met its primary endpoint of progression-free survival (PFS; 22.4 versus 11.5 months, hazard ratio [HR] 0.63, 95% confidence interval [CI]: 0.44 - 0.90) and showed statistically significant improvements in overall response rate (ORR; 82% versus 68%) and very good partial response (VGPR) or better (59% versus 36%) in the venetoclax arm compared to the control arm. However, there were 51 deaths in the safety analysis set, 40 (20.7%) in the venetoclax arm and 11 (11.5%) in the placebo arm (the median overall survival [OS] has not been reached in either arm). The imbalance was predominantly seen in the treatment-emergent deaths which are those occurring on-therapy or within 30 days after the last dose of therapy. Among the 14 treatment-emergent deaths reported, 13 (6.7%) were in the venetoclax arm and 1 (1.0 %) in placebo arm. Of the 13 treatment-emergent deaths in the venetoclax arm, 8 were attributed by investigator to an event of infection; more than half of the deaths were also in the setting of refractory or progressive disease (PD). Although the majority of infection-related deaths occurred within 180 days of starting study treatment, some have occurred later, even after a year or more on treatment. A higher rate of Grade 3 or 4 neutropenia was seen in the venetoclax arm compared to placebo but an association of infection-related deaths with neutropenia has not been established at this point. Among the 37 nontreatment-emergent deaths (those occurring more than 30 days after the last dose of study treatment), 27 (14.0%) were in the venetoclax arm (6 deaths attributed to infection, 3.1%), and 10 (10.4%) in the placebo arm (2 deaths attributed to infection, 2.1%). After the data cutoff of 26 November 2018, additional deaths were reported in the BELLINI trial. As of 01 March 2019, there were 65 deaths in the safety analysis set, 48 (24.7%) in venetoclax arm and 17 (17.5%) in the placebo arm.

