2.2 Benefits and Risks to Patients

Despite recent therapeutic advances, MM remains incurable and is associated with high morbidity and mortality; even with the best available approved agents, all subjects will eventually relapse. Furthermore, the remission duration in R/R MM decreases with each subsequent regimen.⁸

Based on supportive safety and efficacy data from ongoing Phase 1/2 studies of venetoclax as a single agent or in combination with other therapies (see above), subjects enrolled in this study are anticipated to benefit from the combined treatment with pomalidomide based on the pro-apoptotic effects in myeloma cells.

Since the antitumorigenic effects of venetoclax and pomalidomide on myeloma cells are via distinctive mechanisms of action, the combination of these 2 drugs is anticipated to result in an enhanced therapeutic effect that could potentially benefit patients with relapsed MM. The goal of this study is to determine the safety profile, tolerability, and the potential efficacy of venetoclax combined with pomalidomide and dexamethasone in patients with R/R MM.

Following the analysis of the BELLINI study (see Section 2.1), guidance for dose interruption/reduction following a Grade \geq 3 infection or any serious infection in subjects receiving venetoclax have been implemented (see Section 6.4 and Appendix I).

For further details, please see findings from completed studies including safety data in the venetoclax Investigator Brochure⁹ and the pomalidomide package insert.¹⁰

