Deep venous thrombosis, pulmonary embolism, myocardial infarction, and stroke occur in subjects with multiple myeloma treated with pomalidomide. Antithrombotic prophylaxis is recommended for subjects with a history of cardiovascular disease or per investigator discretion. Refer to the pomalidomide package insert for details.¹⁰

Management of Infection

Subjects should receive anti-infective prophylaxis (e.g., amoxicillin/clavulanic acid or levofloxacin or equivalent per institutional guidelines) at least during the first 90 days of study and upon disease

progression for at least 30 days unless contraindicated per investigator discretion. Furthermore, subjects deemed at high risk of infection should receive immunoglobulin replacement therapy (i.e., IVIG) per institutional guidelines or at the investigator's discretion.

The use of antibiotics that are moderate or strong CYP3A inhibitors should be avoided or used with caution and with appropriate venetoclax dose modification (refer to [Appendix I](#)) as per protocol.

All subjects receiving venetoclax should be closely monitored for infections and in the event of a Grade ≥ 3 or serious infection, treatment with venetoclax should be interrupted and upon resolution, treatment can be either resumed at a reduced dose or discontinued, depending on investigator's clinical judgment.

Please refer to [Table 9](#) and [Table 10](#) for guidance on dose interruptions and/or reductions related to venetoclax toxicities.

Potential for drug-drug interactions should be considered. Please refer to [Appendix J](#) for a description of prohibited and cautionary medications.

Management of Other Toxicities

If other events occur that are related to venetoclax or pomalidomide, the investigator may interrupt or dose reduce venetoclax and/or pomalidomide, as appropriate (refer to [Appendix I](#)).

Pomalidomide must be permanently discontinued for angioedema, skin exfoliation, bullae, or any other severe dermatologic reaction.

All subjects should be monitored for new onset hematologic, hepatic, and renal toxicities with dose delay or reduction as appropriate. Please follow local, approved product label or applicable summary of product characteristics¹² for monitoring guidelines for pomalidomide or [Appendix I](#) for venetoclax.

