Increase \geq 25% from baseline	
 • Start or increase rate of IV fluids. • Recheck potassium, phosphorus, uric acid, calcium, and creatinine in 1 to 2 hrs immediately.

ECG = electrocardiogram; IV = intravenous

APPENDIX I. RECOMMENDED DOSE REDUCTIONS RELATED TO DRUG TOXICITIES AND USE WITH CONCOMITANT MEDICATIONS

If a subject reports taking any over-the-counter or prescription medications, vitamins and/or herbal supplements or if administration of any medication becomes necessary from 30 days before the screening visit through 30 days after last dose of study drug, the name of the medication, dosage information including dose, route, and frequency, date(s) of administration including start and end dates, and reason for use must be recorded on the appropriate electronic Case Report Form (eCRF).

Subjects should receive full supportive care during study participation, including transfusion of blood products, fluid and electrolyte replacement, and antibiotics when appropriate. Subjects who use oral contraceptives, hormone-replacement therapy, or other maintenance therapy should continue their use. For guidance regarding medications for management of tumor lysis syndrome (TLS) and neutropenia, refer to Section 6.4.

General guidelines regarding prohibited, cautionary, and allowed medications are summarized in Section 5.3 and Section 5.4. A sample list of prohibited and cautionary medications that may interact with study drugs is provided in [Appendix J](#). It is not possible to produce a complete list of medications that fall into these categories; if in question, please refer to the appropriate product label.

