The AbbVie Therapeutic Area Medical Director (TA MD) identified in [Appendix L](#) should be contacted if there are any questions regarding concomitant or prior therapy(ies) and venetoclax or pomalidomide dose reductions.

Table 9. Study Drug Dose Levels

Dose	Venetoclax	Pomalidomide	Dexamethasone (< 75 years of age)	Dexamethasone (≥ 75 years of age)
Starting dose	800 mg	4 mg	40 mg	20 mg
Dose level –1	600 mg	3 mg	20 mg	12 mg
Dose level –2	400 mg	2 mg	12 mg	8 mg
Dose level –3	200 mg	1 mg	8 mg	4 mg

Table 10. Toxicities Related to Venetoclax

Toxicities	Recommended Action
Grade 3 or Grade 4 neutropenia with infection or fever; or Grade 4 hematologic toxicities (except for lymphopenia)	
 • G-CSF or growth factors for neutropenia should be administered with venetoclax if clinically indicated. • For Grade 4 neutropenia (ANC < 500 cells/μL) without infection, anti-infective prophylaxis (e.g., amoxicillin/clavulanic acid or levofloxacin or equivalent per institutional guidelines) is recommended until the neutropenia improves to Grade 3 or better (ANC > 500 cells/μL). • First episode: Interrupt venetoclax and once the toxicity has resolved to Grade 1 or baseline level, venetoclax may be resumed at the same dose. • For subsequent episodes: Interrupt venetoclax. Consider using G-CSF as clinically indicated. Follow dose reduction guidelines when resuming treatment with venetoclax after resolution. A larger dose reduction may occur at the discretion of the investigator and according to the dose reduction guidelines.
Grade \geq 3 or serious infections	
 • Interrupt venetoclax and upon resolution, treatment can either be resumed at a reduced dose (see Table 9) or discontinued, at the discretion of the investigator.
Grade 3 or 4 non-hematologic events	
 • First episode: Interrupt venetoclax. Once toxicity has resolved to Grade \leq 1 or baseline, venetoclax may be resumed at the same dose. No dose modification is required. • For subsequent episodes: Interrupt venetoclax. Follow dose reduction guidelines when resuming treatment with venetoclax after resolution. A larger dose reduction may occur at the discretion of the investigator and according to the dose reduction guidelines.

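### Venetoclax Table 10 lets the neutropenia row return a subject to full dose after a severe or serious infection, where the infection row and Section 6.4 allow only a lower dose or stopping

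*Protocol*

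**What the plan says.** Three rows of Protocol Appendix I, Table 10 bear on infection.

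- Row 1 is triggered by "Grade 3 or Grade 4 neutropenia with infection or fever; or Grade 4 hematologic toxicities (except for lymphopenia" (closing bracket omitted). For a first episode the action is "Interrupt venetoclax and once the toxicity has resolved to Grade 1 or baseline level, venetoclax may be resumed at the same dose". Later episodes go to the dose-reduction guidelines.
- Row 2 is triggered by any infection that is Grade 3 or higher, or serious. The action is "Interrupt venetoclax and upon resolution, treatment can either be resumed at a reduced dose", with discontinuation as the only alternative. It makes no allowance for a first episode.
- Row 3 is triggered by Grade 3 or 4 non-hematologic events and does not exclude infections. After a first episode, "venetoclax may be resumed at the same dose. No dose modification is required".

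Section 6.4, under Management of Infection, repeats row 2 for everyone on venetoclax: after interruption and resolution, "treatment can be either resumed at a reduced dose or discontinued". Section 2.2 records that, following the Phase 3 analysis, guidance on interruption and reduction after a Grade 3 or higher "infection or any serious infection in subjects receiving venetoclax have been implemented". Appendix I is advisory by its title: "RECOMMENDED DOSE REDUCTIONS RELATED TO DRUG TOXICITIES AND USE WITH CONCOMITANT MEDICATIONS".

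On TLS, Section 6.4 makes dose reduction mandatory for clinical TLS and for clinically significant laboratory TLS. Table 10 resumes the same dose when chemistry changes settle within 24 to 48 hours and a reduced dose when they take longer. Its line requiring reduction whatever the duration names clinical TLS only.

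**The concern.** A neutropenic subject with a serious infection fits rows 1 and 2 equally well, and the rows disagree on whether full dose may be resumed. Neither Appendix I nor Section 6.4 ranks them. The rule that the more specific row governs does not help, because row 1 itself names infection: it is specific to the blood count, and row 2 is specific to the infection's severity. The neutropenia text in Section 6.4 sends the reader to Appendix I without mentioning the infection rule, so a site can arrive at row 1 first and find its case described there.

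What is at stake is a safeguard added for a stated reason. Section 2.1 reports from the Phase 3 study of venetoclax with bortezomib and dexamethasone: "Of the 13 treatment-emergent deaths in the venetoclax arm, 8 were attributed by investigator to an event of infection". Row 1, read alone, permits the full-dose resumption that the later guidance excludes. Safety and tolerability are this study's primary objective, so inconsistent dosing after infection also touches what the study sets out to describe.

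**Working it through.** The plan states no figure on this point, so the check compares triggers and permitted actions, then takes the actions that satisfy every applicable rule.

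| First episode of | Rules that apply | Same dose allowed by | Same dose excluded by |
|---|---|---|---|
| Grade 3/4 neutropenia with Grade 3/4 infection | Rows 1, 2, 3; Section 6.4 | Rows 1, 3 | Row 2, Section 6.4 |
| Grade 3/4 neutropenia with serious infection below Grade 3 | Rows 1, 2; Section 6.4 | Row 1 | Row 2, Section 6.4 |
| Grade 3/4 infection without such neutropenia | Rows 2, 3; Section 6.4 | Row 3 | Row 2, Section 6.4 |
| Grade 3/4 neutropenia with fever only, or with lower-grade non-serious infection | Row 1 | Row 1 | None |

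In the first three cases the common set is a reduced dose or discontinuation. Rows 1 and 3 permit the same dose but do not require it, so reducing breaches nothing. The first two cases are the real conflict. The third is weak, because an infection row is plainly more specific than a generic non-hematologic row. The fourth shows that row 1 keeps a proper use once infection is carved out.

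**Dose difference, from Table 9, assuming the next lower level is used.**

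- Starting dose 800 mg: (800 − 600)/800 = 25% less.
- Part 1, Cohort 1 at 400 mg: (400 − 200)/400 = 50% less.

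**Backstop in Section 6.5.** After a dose-limiting toxicity (DLT), reintroduction is at a reduced dose. DLTs are determined for escalation purposes in the first 28 days, and later events only *may* count. Events the investigator attributes to concurrent illness are excluded. Section 2.1 places most infection-related deaths in the Phase 3 study within 180 days and some after a year or more, so the DLT rule covers only part of the period of interest.

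**TLS.**

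- Clinically significant laboratory TLS that resolves within 48 hours: Section 6.4 requires reduction, whereas Table 10's same-dose line applies and its reduction line does not reach the event. This is a genuine but small mismatch. In Cycle 1 it is partly covered, because such an event is a listed DLT.
- Changes lasting longer: Sections 6.4 and 6.5 confine the no-reduction allowance to changes lasting under 48 hours, the same limit as Table 10. The 72 hours in that allowance is the permitted length of interruption. The only timing difference left is that, for TLS unresolved at 72 hours, those sections ask that a reduction be considered, whereas Table 10 says to resume at a reduced dose.

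**The case against.** The strongest reply is that the protocol body already decides the case. Section 6.4 speaks to all subjects on venetoclax, row 2 repeats it, and Section 2.2 states the intent and points to both places. Rows 1 and 3 are permissive, and a site resuming full dose would depart from row 2 and Section 6.4. Other protections also operate. Table 11 interrupts pomalidomide and resumes it at 3 mg after an ANC below 0.5 × 10⁹/L or febrile neutropenia. Anti-infective prophylaxis is advised for at least the first 90 days, with immunoglobulin for those at high risk. A Safety Review Committee reviews data periodically, and dose questions can go to the sponsor's medical director.

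Most of this stands, and it rules out several stronger readings that a reader might infer:

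- *That the protocol as a whole authorizes full dose after a serious infection.* It does not; only row 1, and more weakly row 3, do so when read alone.
- *That the Phase 3 deaths measure the harm.* They do not. Section 2.1 ties none of them to same-dose resumption, says more than half of the venetoclax-arm treatment-emergent deaths were also in refractory or progressive disease, and says no association between neutropenia and infection-related deaths has been established.
- *That Table 10 and Section 6.4 contradict each other on TLS lasting 48 to 72 hours.* They do not, because the allowance in Section 6.4 stops at 48 hours.

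The reply does not remove the row 1 overlap. The other protections do not set the venetoclax dose, and a site that finds its case in row 1 may see no question to ask.

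**Conclusion.** The point holds as an inconsistency in a safety rule that should be corrected. Row 1 of Table 10 permits full-dose resumption in a case that row 2 and Section 6.4 exclude, and no precedence is stated. The intended rule is reasonably clear and a compliant action always exists, which limits the weight. The row 3 overlap and the TLS mismatch are secondary.

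For a subject in the overlap, the choice is between 800 mg and 600 mg or lower, or stopping; at 400 mg it is between 400 mg and 200 mg, or stopping. This assumes a first episode and a step to the next Table 9 level. How many subjects would be affected cannot be computed, since the documents give no rate for Grade 3/4 neutropenia coinciding with a Grade 3 or higher or serious infection. The exact ORR tests, the sample size and the Bayesian optimal interval escalation rules are unaffected.

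**What to change.** 1. Add one sentence to Table 10: *For any Grade ≥ 3 or serious infection, with or without neutropenia, the infection row governs over the neutropenia and non-hematologic rows.*
2. Limit row 1's same-dose resumption to fever without such an infection, lower-grade non-serious infection, or Grade 4 hematologic toxicity, with DLTs following Section 6.5.
3. Minor: extend Table 10's duration-independent TLS line to *clinical TLS or clinically significant laboratory TLS*, to match Section 6.4. The remaining 72-hour wording in Sections 6.4 and 6.5 can be brought into line with Table 10 at the same time.

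The cost is a few sentences. Section 8.1 requires IEC/IRB approval of any amendment, so the changes can travel with the next one. No visits, procedures or subjects are added. The downside is that some subjects would resume at a lower dose than row 1 alone would permit, which is what row 2 already intends.

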5.4 Prior and Concomitant Therapy

Any medication or vaccine (including over-the-counter or prescription medicines, vitamins, and/or herbal supplements) that the subject is receiving from 30 days before and throughout screening or receives during the study and up to 30 days after last dose of study drug must be recorded in the electronic case report form (eCRF). Any prior transfusions (blood or platelet) must be recorded in the eCRF and the investigator must ensure that this data is consistent with the subject's medical history.

The following medications are allowed **after Part 1, Cycle 1** and for Part 2 (dose expansion) to **use with caution** if no appropriate therapeutic alternative exists (additional guidance noted):

- Strong and moderate CYP3A inhibitors (venetoclax dose reductions)
- Strong CYP1A2 inhibitors (pomalidomide dose reductions)
- Strong and moderate CYP3A inducers (avoid)

Recommended venetoclax and pomalidomide dose modifications when administered concomitantly with strong or moderate CYP3A inhibitors and strong CYP1A2 inhibitors are provided in [Appendix I](#).

The following medications to **use with caution** include:

- warfarin (closely monitor international normalized ratio)
- P-glycoprotein (P-gp) substrates
- breast cancer resistance protein (BCRP) substrates
- organic anion-transporting polypeptide (OATP)1B1/1B3 substrates
- P-gp inhibitors
- BCRP inhibitors
- high-dose corticosteroids

Specific examples of prohibited and cautionary medications that fall into these categories can be found in [Appendix J](#).

Subjects should be advised that cigarette smoking reduces pomalidomide exposure because of CYP1A2 induction and therefore may reduce efficacy.

Herbal and natural remedies are to be avoided while on study drug.

Any questions regarding prior or concomitant therapy should be raised to the AbbVie emergency contact. Information regarding potential drug interactions with venetoclax or pomalidomide can be located in the Investigator's Brochure or package insert, respectively.

While on study, unless prohibited by the protocol, subjects should receive best supportive care per investigator discretion. Supportive care and medications that may be required for venetoclax and/or pomalidomide during the study include the following:

- allopurinol or other appropriate tumor lysis syndrome (TLS) risk-reducing agent
- adequate fluids to ensure dehydration prevention (note: per institutional standards while using medical judgment)

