It is recommended that subjects should receive anti-infective prophylaxis (e.g., amoxicillin/clavulanic acid, levofloxacin, or equivalent per institutional guidelines) at least during the first 90 days of study, when Grade 4 neutropenia develops (ANC $<$ 500 cells/ μ L) and continued until the neutropenia improves to Grade 3 or better (ANC $>$ 500 cells/ μ L), and upon disease progression for at least 30 days, unless contraindicated per investigator discretion. Furthermore, it is recommended that subjects deemed at high risk of infection receive immunoglobulin replacement therapy (i.e., intravenous immunoglobulin [IVIG]) per institutional guidelines or at the Investigator's discretion. Pneumocystis prophylaxis is allowed per institutional guidelines or at the investigator's discretion.

- The use of antibiotics that are moderate or strong CYP3A4 inhibitors should be avoided or used with caution and with the appropriate venetoclax dose modification ([Appendix I](#)) as per protocol.

Pneumococcal and Influenza Vaccination

Pneumococcal vaccination may be considered during the initiation of screening procedures for all subjects who have not previously received the vaccine. At the investigator's discretion, influenza vaccination may also be considered (live attenuated vaccines are not allowed) during the initiation of screening procedures and while on study treatment.

Tumor Lysis Syndrome Prophylaxis

There is a potential for TLS in subjects affected by hematologic malignancies. Refer to Section 6.4 for required TLS prophylaxis.

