Concomitant administration of moderate or strong cytochrome P450 (CYP)3A and strong CYP1A2 inhibitors is prohibited during Part 1 (dose escalation), Cycle 1. Use of strong or moderate CYP3A inhibitors and strong CYP1A2 inhibitors is allowed (with appropriate venetoclax and pomalidomide dose reductions, respectively) after Part 1 (dose escalation), Cycle 1 and throughout the study for subjects enrolled in Part 2 (dose expansion) if no appropriate therapeutic alternative exists. Venetoclax dose reductions for concomitant administration with moderate or strong CYP3A inhibitors are presented in [Table 7](#). Subjects should be monitored more closely for signs of toxicities and the venetoclax dose may need to be further reduced. Pomalidomide dose reductions for concomitant use with strong CYP1A2 inhibitors are presented in [Table 8](#). Subjects should be monitored more closely for signs of toxicities and the venetoclax dose may need to be further reduced. After discontinuation of the CYP3A inhibitor, wait for 3 days before venetoclax dose is increased back to the target dose.

Concomitant administration of moderate or strong CYP3A inducers is prohibited during Cycle 1 (dose escalation), Part 1. After completion of Cycle 1 (dose escalation), Part 1, and throughout the study for subjects enrolled in Part 2 (dose expansion), concomitant use of moderate or strong CYP3A inducers should still be avoided. Alternative treatments with less CYP3A induction should be considered.

Study drug dose levels are presented in [Table 9](#). Toxicities related to venetoclax, pomalidomide, and dexamethasone are presented in [Table 10](#), [Table 11](#), and [Table 12](#), respectively.

Table 7. Dose Modifications for Venetoclax with Concomitant Moderate and Strong CYP3A Inhibitor Use

Venetoclax Dose with No Moderate or Strong CYP3A Inhibitor	Venetoclax Dose if Co-Administered with a Moderate CYP3A Inhibitor	Venetoclax Dose if Co-Administered with a Strong CYP3A Inhibitor
400 mg	200 mg	100 mg
600 mg	300 mg	100 mg
800 mg	400 mg	200 mg

CYP = cytochrome P450

Table 8. Dose Modifications for Pomalidomide with Concomitant Strong CYP1A2 Inhibitor Use

Assigned Pomalidomide Dose	Pomalidomide Dose if Co-Administered with a Strong CYP1A2 Inhibitor
4 mg	2 mg

CYP = cytochrome P450

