
Warfarin**
 
P-gp substrates – aliskiren, ambrisentan, colchicine, dabigatran etexilate, digoxin, everolimus,* fexofenadine, lapatinib,* loperamide, maraviroc, nilotinib,* ranolazine, saxagliptin, sirolimus,* sitagliptin, talinolol, tolvaptan, toptecan*
 
BCRP substrates – methotrexate,* mitoxantrone,* irinotecan,* lapatinib,* rosuvastatin, sulfasalazine, toptecan*
 
OATP1B1/1B3 substrates – atrasentan, atorvastatin, ezetimibe, fluvastatin, glyburide, rosuvastatin, pitavastatin, pravastatin, repaglinide, simvastatin acid, telmisartan, valsartan, olmesartan
 
P-gp inhibitors – amiodarone, azithromycin, captopril, carvedilol, dronedarone, felodipine, quercetin, quinidine, ronalzine, ticagrelor
 
BCRP inhibitors – gefitinib*
 
Corticosteroids – cortisone, hydrocortisone, methylprednisolone, prednisolone, prednisone, triamcinolone, betamethasone, dexamethasone

BCRP = breast cancer resistance protein; CYP = cytochrome P450; FDA = Food and Drug Administration; OATP = organic anion-transporting polypeptide; P-gp = P-glycoprotein; USPI = United States package insert

a. Moderate CYP3A inhibitor per venetoclax FDA USPI.

* These are anticancer agents; contact the AbbVie Therapeutic Area Medical Director before use.

** Closely monitor the international normalized ratio.

† If a subject requires use of these medications, use with caution and reduce the venetoclax dose by 75%. After discontinuation of the CYP3A inhibitor, wait for 3 days before venetoclax dose is increased back to the target dose.

‡ If subject requires use of these medications, use with caution and reduce the venetoclax dose by 50%. After discontinuation of CYP3A inhibitor, wait for 3 days before venetoclax dose is increased back to the target dose.

†† If a subject requires use of these medications, use with caution and reduce the pomalidomide dose by 50%.

Note: this is not an exhaustive list. For an updated list, see the following link:

<http://www.fda.gov/Drugs/DevelopmentApprovalProcess/DevelopmentResources/DrugInteractionsLabeling/ucm093664.htm>

In addition to the medications listed in this table, subjects receiving venetoclax should not consume grapefruit, grapefruit products, Seville oranges (including marmalade containing Seville oranges), or Star fruits. Herbal and natural remedies are to be avoided.

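### At venetoclax 600 mg with a strong CYP3A inhibitor, the Appendix J note implies 150 mg (1.5 tablets) while Table 7 gives 100 mg

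*Protocol*

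**What the plan says.** The Protocol deals with venetoclax dosing alongside a strong CYP3A inhibitor in two places.

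- **Appendix I, Table 7.** The column headed "Venetoclax Dose if Co-Administered with a Strong CYP3A Inhibitor" gives 100 mg, 100 mg and 200 mg for subjects otherwise on 400 mg, 600 mg and 800 mg. The text above it states: "Venetoclax dose reductions for concomitant administration with moderate or strong CYP3A inhibitors are presented in" Table 7. Section 5.4 likewise says: "Recommended venetoclax and pomalidomide dose modifications when administered concomitantly with strong or moderate CYP3A inhibitors and strong CYP1A2 inhibitors are provided in" Appendix I. Its anti-infective paragraph adds that antibiotics which inhibit the enzyme "should be avoided or used with caution and with the appropriate venetoclax dose modification", again citing Appendix I. Section 6.4 (Management of Infection) makes the same reference.
- **Appendix J, dagger note.** For the listed strong inhibitors the instruction is to "use with caution and reduce the venetoclax dose by 75" per cent. A parallel note gives a 50% cut for moderate inhibitors. Neither note mentions Table 7 or rounding. Sites reach this appendix for the drug lists; Section 5.4 says: "Specific examples of prohibited and cautionary medications that fall into these categories can be found in" Appendix J. Sections 5.3 and 6.4 also point there.

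After Cycle 1 of Part 1, these inhibitors are permitted, and they are permitted "throughout the study for subjects enrolled in Part 2 (dose expansion) if no appropriate therapeutic alternative exists".

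**The concern.** The dagger note reads as a complete dosing instruction, and it stands beside the drug list that a site consults when a subject needs one of these medicines. At 600 mg it disagrees with Table 7 and asks for a dose that cannot be made from whole tablets.

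The situation is foreseeable. Table 7 has its own 600 mg row. After a Grade 3 or higher or serious infection, Table 10 has venetoclax interrupted and then either stopped or resumed at a reduced dose, and one level below 800 mg is 600 mg. The strong inhibitors in Appendix J include anti-infectives such as clarithromycin, posaconazole and voriconazole.

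A site working from the note alone would have to round. Rounding up gives 200 mg, the dose Table 7 assigns at the unreduced 800 mg level. The step down to level -1 would then have no effect while the inhibitor is taken.

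**Working it through.** **Inputs**

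- Strong inhibitor: 75% cut, so 0.25 × dose (Appendix J, dagger note).
- Moderate inhibitor: 50% cut, so 0.50 × dose (Appendix J, companion note).
- Listed reduced doses: Table 7, Appendix I.
- Venetoclax dose levels: 800 mg at start, then 600, 400 and 200 mg (Table 9, Appendix I).
- Tablet strength: 100 mg only (Table 2, Section 5.7).

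**Appendix J percentages against Table 7**

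| Dose without inhibitor | Moderate: 0.50 × dose | Table 7 | Strong: 0.25 × dose | Table 7 |
|---|---|---|---|---|
| 400 mg | 200 mg | 200 mg | 100 mg | 100 mg |
| 600 mg | 300 mg | 300 mg | **150 mg** | **100 mg** |
| 800 mg | 400 mg | 400 mg | 200 mg | 200 mg |

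Five of the six cells are reproduced exactly. The exception is 600 mg with a strong inhibitor, where the difference is 150 − 100 = 50 mg.

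**Cut implied by Table 7 at 600 mg:** 1 − 100/600 = 83.3%.

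**Tablets needed under the note at 600 mg:** 150/100 = 1.5.

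**Whole-tablet choices at 600 mg**

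- 100 mg: an 83.3% cut, equal to Table 7.
- 200 mg: 1 − 200/600 = 66.7%, short of 75%; 200/100 = 2.0 times the Table 7 dose.

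**Level -3 (200 mg), for completeness:** 0.25 × 200 = 50 mg, less than one tablet. Table 7 has no row for 200 mg.

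**The case against.** The strongest reply is that nothing was miscalculated. The note states a general percentage, Table 7 is the look-up table, and its 100 mg is what 150 mg becomes when taken down to a whole tablet. Sections 5.4 and 6.4 and Appendix I send sites to Appendix I for the dose, whereas Appendix J is titled a sample list and is cited for drug names. Questions on dose reductions go to the sponsor's medical director. Rounding up to 200 mg would break the note's own 75%, and Appendix I points the other way, warning that "the venetoclax dose may need to be further reduced". Table 7 itself gives one dose, 100 mg, to both the 400 mg and 600 mg levels, so two levels sharing a dose is not harmful in itself.

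Much of this stands. Table 7 governs, the 200 mg outcome is unlikely, and the problem is better described as an internal inconsistency than as an arithmetic error. Two things remain. The rounding explanation is an inference, since no text in the Protocol states it. And the note is worded as a dosing rule, not as background, yet carries no pointer to the table that overrides it. As to shared doses, Table 7 merges 600 mg downward, to the dose for level -2; rounding up would merge it with the starting level, the opposite direction.

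**Conclusion.** The Protocol gives two conflicting doses for the same subject: 150 mg from the Appendix J note and 100 mg from Table 7, in one of six cells. Table 7 is the intended and dispensable dose; the note is wrong as written at 600 mg.

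The impact is minor. It reaches only subjects reduced to 600 mg who need a strong CYP3A inhibitor and have no suitable alternative. The documents give no expected number of such subjects; on the assumption that they are few, any effect on the Part 2 response rate tests should be negligible. The Cycle 1 DLT assessment is unaffected, because these inhibitors are prohibited in Cycle 1 of Part 1 (Section 5.3). No sample size, power or significance level depends on this point.

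**What to change.** Reword the Appendix J dagger note to: *reduce the venetoclax dose by at least 75%, per Table 7 (Appendix I)*. This fits all three strong-inhibitor rows (75%, 83.3%, 75%) and changes no listed dose. A bare reference to Table 7 would also remove the conflict.

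The cost is one footnote line. Section 8.1 requires ethics committee approval for any amendment, so the edit can wait for the next one planned.

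The missing 200 mg row in Table 7 is a separate question for the sponsor's clinical team. Neither wording answers it, and it could usefully be settled in the same amendment.
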